1.0 INTRODUCTION

1.1 HPV/p16 negative SCC-HN

There are well studied standard treatment approaches, both operative based, and non-operative based, for patients with squamous cell cancer of the head and neck (SCC-HN).¹⁻³ The great majority of patients who present with locally advanced SCC-HN are treated with definitive chemoradiotherapy (CRT).⁴ Recent studies have emerged indicating that human papillomavirus (HPV) and/or p16 associated SCC of the oropharynx is increasing in incidence and has a biologically distinct pathogenesis and response to treatment than other head and neck cancers.^{5,6} These patients have superior disease control rates and overall survival compared to the more traditional non-viral associated cancers. Patients with HPV/p16 negative disease, however, have inferior locoregional control rates when treated with standard chemoradiotherapy and clinical trials are currently investigating the addition of transoral robotic surgery or targeted systemic agents in an effort to intensify the current standard of care and improve outcomes.^{7,8}

1.2 High risk patients ineligible for standard therapy

Among the HPV/p16 negative population, there is a subset of patients who are high risk for poor outcomes as they are ineligible for standard of care chemoradiotherapy, either due to advanced age, co-morbid illnesses, or because of patient refusal. These patients present a clinical challenge as their disease calls for very aggressive therapy, but patient factors precludes this possibility and often relegates them to substandard treatment options. In our practice, some of these high risk patients are treated with full course radiation, potentially with a targeted agent, some with a split course radiation approach and simply offered palliative treatment approaches. For those who undergo conventional 6-7 weeks of radiotherapy, treatment can be difficult to complete and be associated with significant morbidity. Loco-regional control outcomes are also inferior at 30-60%.⁹⁻¹¹

As such, shorter, more tolerable, and potentially more effective treatments are needed in this high risk patient population with HPV/p16 negative SCC-HN.

1.3 *Stereotactic Body Radiation Therapy (SBRT) in head and neck cancer*

Stereotactic body radiotherapy (SBRT) is a technique that employs highly focused external beam radiation delivered in large doses over 1-5 treatments and has become a standard treatment approach for a variety of tumor types and clinical scenarios (e.g. medically inoperable lung cancer).¹² SBRT has become increasingly utilized in SCC-HN in patients who have recurrent previously irradiated disease. Doses most commonly employed range from 30-50 Gray (Gy) in 5 fractions (fx), with locoregional disease recurrence rates of 30-50%. Grade 3-5 toxicity can be significant including soft tissue or bone necrosis, fibrosis, dysphagia, carotid blowouts, and fistulization, and range from 3-18% among several series.¹³ The University of Pittsburgh has the most extensive experience with this technique and has performed the only phase I dose escalation study testing the safety of SBRT in previously irradiated SCC-HN. They successfully escalated doses up to 44Gy in 5 fx without encountering grade 3-5 toxicity.¹⁴ They have went on to treat >150 patients with ≥ 40 Gy, without excessive morbidity.¹⁵ We have treated 12 patients with SBRT in the reirradiation setting with varying doses of 35Gy in 5 fractions up to 45Gy in 5 fractions. Our preliminary experience suggests that it is feasible, planning according to traditional constraints is achievable and the short term toxicities are quite mild. We are awaiting maturity of our experience to assess long term severe late effects.

A summary of SBRT reirradiation studies in head and neck cancer are depicted in the following table:

Efficacy and Toxicity of Definitive Head and Neck SBRT Re-irradiation							
Study	Number of Patients	SBRT Dose/ #fractions	Median f/u (months)	Median Survival/ 1y OS	Response Rate (CR+PR)	Local-Regional Progression	Toxicity

Siddiqui, et al (2009) ¹⁶	29	36-48Gy 5-8fx	36	7 mths 38%	69	4%	14% grade ≥ 3 (dysphagia, cataract, pain); 14% grade 4 (fistula/ulceration)†
Roh, et al. (2009) ¹⁷	44 (35 evaluable)	18-40Gy 3-5fx	17	16 mths 52%	80%	11%	10% grade ≥ 4 (soft tissue/bone necrosis/death)
Unger, et al. (2010) ¹⁸	38	21-35Gy 2-5fx	16	20 mths 40%	80%	32%	12% grade 4/5 (arterial bleed, death, fistula, soft tissue necrosis, dysphagia, trismus, cranial neuropathy)
Kodani, et al. (2011) ¹⁹	21*	20-42Gy 3-8fx	28	16 mths 70%	62%	14%	28% late \geq grade 3 (hemorrhage and death X 2, mucositis, skin necrosis, chronic ulcer)
Cengiz, et al. (2011) ²⁰	46 (37 evaluable)	18-35Gy 1-5fx	7	12 mths 46%	57%	13.5%	13% carotid blowout (7/8 died)‡ 13% late \geq grade 2 (Soft tissue/bone necrosis, dysphagia)
Comet, et al. (2012) ²¹	40	36Gy 6fx	26	14 mths 58%	79	23%	10% grade 3 (mucositis, dysphagia, fibrosis).
Vargo, et al. (2014) ²²	132	35-50Gy 5fx	6	7 mths 49%	75%**	44%	7% grade 3 (Dysphagia, Pain and Skin). No grade 4/5
OS = overall survival; † All fistulas occurred in the setting of tumor recurrence/progression rather than due to SBRT toxicity. ‡ All pts with carotid blowout had tumor completely surrounding carotid arteries, with no constraints applied to avoid the vessels. No patient with carotid artery dose $< 100\%$ had CBO and only patients with > 180 degrees of CA involved had CBO. * Includes only those patients with prior radiation. ** While not reported in this series, this rate was culled from several previous published reports from the UPitt experience.							

While SBRT in the re-irradiation setting has been shown to be safe with reasonable control rates, this technique has not been formally studied in the radiation naïve patient. As such, we propose a phase I dose escalation study in high risk patients who are ineligible/refuse standard of care therapy as a means of assessing the safety of such treatment in patients who may have prolonged survival compared to re-irradiation

patients. We will also evaluate the efficacy of this far more tolerable and convenient regimen than our current commonly used approaches for these patients.

1.4 *Proposal*

We propose to conduct a phase I dose escalation trial of SBRT in high risk patients with locally advanced head and neck cancer who are ineligible/refuse standard chemoradiotherapy.

2.0 OBJECTIVES

2.1 Primary Objective: To explore the maximum tolerated dose of head and neck SBRT in a high risk patient population ineligible for standard chemoradiotherapy. Two dose levels will be used 40Gy, 45Gy all in 5 fractions.

2.2 Secondary Objectives:

- 2.2.1 Assess profiles of SBRT toxicity and examine patient (including co-morbidities), tumor and treatment related factors that are associated with SBRT related toxicity
- 2.2.2 identify any dose volume parameters that are associated with SBRT related toxicity
- 2.2.3 explore potential dose response relationships between higher SBRT dosing and radiographic response
- 2.2.4 assess impact of SBRT on patients quality of life

Dose limiting toxicities in this study will be defined as grade 4/5 toxicity:

- soft tissue or bone necrosis
- carotid blowout or other treatment related bleed
- aspiration
- infection
- fistula that is deemed as life threatening.

While grade 3 toxicities will be recorded as SAEs and reported as per IRB guidelines, they will not be considered DLTs or influence the dose escalation component of the study, given the high risk nature of the disease and the associated morbidities of uncontrolled disease.

3.1.7 All grade 3 toxicities will be recorded as serious adverse events but will not be scored as DLT, as these are somewhat expected and most often reversible complications associated with radiotherapy. Grade 1/2 events will be recorded, but will not be considered serious adverse events.

3.1.8 Symptoms and morbidity attributed to disease progression, as determined by the treating physician, and another co-investigator of the study, will not be considered a toxicity that will influence the dosing schema.

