8.2 Definitions

8.2.1 Adverse Events

An **adverse event** (AE) is any unfavorable or unintended event, physical or psychological, associated with a research study, which causes harm or injury to a research participant as a result of the participant's involvement in a research study. The event can include abnormal laboratory findings, symptoms, or disease associated with the research study. The event does not necessarily have to have a causal relationship with the research, any risk associated with the research, the research intervention, or the research assessments.

Adverse events may be the result of the interventions and interactions used in the research; the collection of identifiable private information in the research; an underlying disease, disorder, or condition of the subject; and/or other circumstances unrelated to the research or any underlying disease, disorder, or condition of the subject. In general, adverse events that are at least partially the result of (a) or (b) would be considered related to the research, whereas adverse events solely related to (c) or (d) would be considered unrelated to the research.

8.2.2 The significance of an adverse event is used to describe the patient/event outcome or action criteria associated with events that pose a threat to a patient's life or functioning (i.e., moderate, severe or life threatening). Based on the National Cancer Institute Guidelines for the Cancer Therapy Evaluation Program, severity can be defined by the following grades of events:

Grades 1 are mild adverse events. (e.g., minor event requiring no specific medical intervention; asymptomatic laboratory findings only; marginal clinical relevance)

Grades 2 are moderate adverse events (e.g., minimal intervention; local intervention; non-invasive intervention or elective interventional radiological procedure; transfusion;).

Grades 3 are severe and undesirable adverse events (e.g., significant symptoms requiring hospitalization or invasive intervention; transfusion; therapeutic endoscopy or operation).

Grades 4 are life threatening or disabling adverse events (e.g., complicated by acute, life-threatening metabolic or cardiovascular complications such as circulatory failure, hemorrhage, sepsis; life-threatening physiologic consequences; need for intensive care or

emergent invasive procedure; emergent interventional radiological procedure, therapeutic endoscopy or operation).

Grades 5 are fatal adverse event resulting in death.

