8.2.3 Serious Adverse Events

A **serious adverse event** (SAE) is any adverse experience occurring at any dose that results in any of the following outcomes:

- Results in **death**.
- Is a **life-threatening** adverse experience. The term life-threatening in the definition of serious refers to an adverse event in which the subject was at risk of death at the time of the event. It does not refer to an adverse event which hypothetically might have caused death if it were more severe.
- Requires **inpatient hospitalization or prolongation of existing hospitalization**. Any adverse event leading to hospitalization or prolongation of hospitalization will be considered as Serious, UNLESS at least one of the following expectations is met:
 - The admission results in a hospital stay of less than 12 hours OR
 - The admission is pre-planned (i.e., elective or scheduled surgery arranged prior to the start of the study) OR
 - The admission is not associated with an adverse event (e.g., social hospitalization for purposes of respite care).

However it should be noted that invasive treatment during any hospitalization may fulfill the criteria of “medically important” and as such may be reportable as a serious adverse event dependant on clinical judgment. In addition where local regulatory authorities specifically require a more stringent definition, the local regulation takes precedent.

- Results in **persistent or significant disability/incapacity**. The definition of disability is a substantial disruption of a person’s ability to conduct normal life’s functions.
- Is a **congenital anomaly/birth defect**.
- Is an **important medical event**. Important medical events that may not result death, be life-threatening, or require hospitalization may be considered a serious adverse experience when, based upon appropriate medical judgment, they may jeopardize the patient or subject and may require medical or surgical intervention to prevent one of the outcomes listed in this definition. Examples of such medical events include allergic bronchospasm requiring intensive treatment in an emergency room or at home, blood disease or disorders, or convulsions that do not result in inpatient hospitalization, or the development of drug dependency or drug abuse.

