8.5 Data Safety Toxicity Committee

It is the Case Comprehensive Cancer Center's Principal Investigator's responsibility to ensure that ALL serious adverse events are reported to the Case Comprehensive Cancer Center's Data Safety Toxicity Committee. This submission is simultaneous with their submission to the Sponsor or other Regulatory body.

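### Section 3.1.7 bars grade 1/2 events from serious status without exception, while 8.2.3 decides seriousness by outcome whatever the grade, and no section says which rule governs

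*Combined protocol and SAP*

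**What the plan says.** Two parts of the protocol define what is serious.

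Section 3.1.7 (Dose Escalation) works by grade. For grade 3: "All grade 3 toxicities will be recorded as serious adverse events but will not be scored as DLT". Section 3.1.6 says the same and adds reporting under IRB guidelines. For lower grades: "Grade 1/2 events will be recorded, but will not be considered serious adverse events".

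Section 8.2.3 (Serious Adverse Events) works by outcome. An SAE "is any adverse experience occurring at any dose that results in any of the following outcomes", and the list covers death, threat to life, hospitalisation, disability, congenital anomaly and important medical events. On hospitalisation it says: "Any adverse event leading to hospitalization or prolongation of hospitalization will be considered as Serious, UNLESS" one of three exceptions applies: a stay under 12 hours, a pre-planned admission, or an admission not linked to an adverse event.

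Reporting follows SAE status. Section 8.4 sends SAEs, from consent to thirty days after the last dose, to the principal investigator. Section 8.5 makes it that investigator's duty "to ensure that ALL serious adverse events are reported to the Case Comprehensive Cancer Center's Data Safety Toxicity Committee". Section 8.3 covers adverse events generally: treatment-related events are recorded with grade, attribution, action and outcome, and adverse events go to the IRB under its policies.

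Grading is by CTCAE v4.0 (3.1.6, 6.4, 8.1.1, 8.3). Section 8.2.2 also gives general descriptions of each grade.

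**The concern.** Grade measures severity; seriousness, as 8.2.3 defines it, depends on what happened to the patient. The last sentence of 3.1.7 uses the first to rule out the second. For some low-grade events the two sections therefore give opposite answers, and staff have no stated order of precedence.

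What is at stake is oversight. The only routes to the principal investigator and the safety committee written in the protocol are for SAEs. An event that 3.1.7 removes from that class loses both. This is a phase I study with safety as its primary endpoint, in patients who may be elderly or have other illnesses (1.2) and who are eligible from a Karnofsky score of 40 (4.1.6). Admission after a moderate event is plausible in such patients.

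**Working it through.** No arithmetic applies, since the point rests on wording. The check is to take each type of event through both sections.

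| Event | By 3.1.7 | By 8.2.3 | Can both be followed? |
|---|---|---|---|
| Grade 1/2, unplanned admission of 12 hours or more because of the event | Not an SAE | SAE | No |
| Grade 1/2, prolongs an existing hospitalisation | Not an SAE | SAE | No |
| Grade 1/2, judged an important medical event | Not an SAE | SAE | No |
| Grade 1/2, admission under one of the three exceptions, no other criterion met | Not an SAE | Not an SAE | Yes |
| Grade 3 toxicity, no listed outcome | SAE | Not an SAE by outcome | Yes, if 3.1.7 is read as adding to 8.2.3 |
| Grade 3 toxicity with a listed outcome | SAE | SAE | Yes |
| Grade 4/5 | Not addressed | SAE if fatal, life-threatening or disabling | Yes |

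The conflict is confined to the first three rows.

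Step 1: does any text resolve it? Low grade is not among the three hospitalisation exceptions. Section 8.2.3 gives way to local regulation only where that is stricter. The last sentence of 3.1.7 is neither a local regulation nor stricter. No other section sets an order of precedence.

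Step 2: what follows if 3.1.7 is applied? Events in the first three rows fall outside the SAE reporting of 8.4 and 8.5. They still fall under the recording clause of 3.1.7 itself and, if treatment-related, under the full recording required by 8.3. The IRB route in 8.3 also remains.

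Step 3: how wide is the gap? Section 8.2.2 gives symptoms requiring hospitalisation as an example of grade 3 and describes disabling events as grade 4. On that scale many admitted patients would already have a grade 3 event, which 3.1.7 counts as serious. But 8.2.2 offers examples, not a rule, and CTCAE v4.0 sets the grade. Prolongation of a stay appears in none of its grade descriptions, and important medical events rest on judgment and need not involve admission. Section 8.2.2 also lists transfusion under grade 2 ("non-invasive intervention or elective interventional radiological procedure; transfusion") and again under grade 3. Anyone grading from that text could place the same transfused event in either grade, and 3.1.7 would then let that choice decide SAE status.

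Step 4: does it reach the dose decisions? DLTs are restricted to specified grade 4/5 toxicities (3.1.6), so grade 1/2 events never count towards them.

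**The case against.** The best defence is that the gap is small and the safeguards are real. Section 8.2.2 puts most hospitalised toxicities at grade 3 or above, the events are recorded, the IRB route exists, and CTCAE v4.0 is already the named grading instrument. All of this stands and limits the consequence. It does not remove the contradiction, because admission, prolongation and important medical events at grade 1/2 remain possible. The Data and Safety Monitoring Plan invoked in 11.2.5 may contain a further route to the committee, but its content is not in the documents.

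A reader might infer more than the text supports:

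- **That the events are lost.** They are not. Section 3.1.7 itself requires them to be recorded. The loss is of SAE status and the reporting tied to it.
- **That low-grade disabling events are a main case.** Section 8.2.3 sets no grade for disability ("The definition of disability is a substantial disruption" of normal life functions), but 8.2.2 describes disabling events as grade 4, so this example is weak.
- **That the size can be read from the re-irradiation table in 1.3.** Rates of 7% and 28% would give 0.07 × 18 = 1.3 and 0.28 × 18 = 5.0 patients. These figures do not measure the problem. The 7% is a grade 3 rate. The 28% is a late rate for grade 3 or higher that includes two deaths, which are SAEs under 8.2.3 anyway. Both come from previously irradiated patients, and neither counts grade 1/2 events with a serious outcome.
- **That the grade 3 rule is also a contradiction.** Staff can satisfy both sections by reporting everything that meets 8.2.3 plus all grade 3 toxicities. That is a defensible cautious choice. Removing the label would take away the written committee route for grade 3 toxicities that meet no listed outcome.
- **That SAE comparisons between 40 and 45 Gy would be distorted.** The documents plan no SAE table by dose level. Section 12.0 analyses DLTs and grade 3 events, not SAE status.

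**Conclusion.** The contradiction holds, and it runs in one direction: the last sentence of 3.1.7 excludes from SAE status some grade 1/2 events that 8.2.3 makes serious. If it is followed, those events are not reported as SAEs to the principal investigator or the Data Safety Toxicity Committee.

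The documents give no rate for such events, so the number affected cannot be estimated. It is probably small. The conclusion assumes that staff may apply 3.1.7 as written and that no plan outside these documents overrides it. The maximum tolerated dose, the escalation and stopping rules, and the planned analyses are not affected. This is a defect in safety reporting. It deserves correction because a stated rule gives the wrong classification and the remedy is cheap.

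**What to change.** Amend 3.1.7 so that its last sentence applies only where 8.2.3 is not met, or delete that sentence. Qualifying it has the advantage of keeping the instruction to record grade 1/2 events; if it is deleted, that instruction should be kept elsewhere, since 8.3 requires full recording only of treatment-related events.

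Add a statement that 8.2.3 decides seriousness whatever the grade, and that all grade 3 toxicities are SAEs in addition, as 3.1.6 and 3.1.7 already provide.

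Optionally, state in 8.2.2 that CTCAE v4.0 sets the grade and that the descriptions there are illustrative, since transfusion appears under two grades.

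The cost is a short amendment and possibly a few more SAE reports. Sample size, visits and dose decisions do not change.

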3.2 Patient Enrollment

We plan on enrolling a maximum of 18 patients to this study. This relies on the traditional 3+3 approach used in many chemotherapy phase I studies, but we have doubled the number in each arm to ensure we capture potential toxicities which can be delayed.

3.3 Expected Duration of Subject Participation

3.3.1 PreSBRT visits for dental evaluation (if indicated) and simulation. 5 visits for treatment over a 1.5 to 3 week time period.

3.3.2 Patients will be followed for one year after SBRT. All patients will be seen at least at 0.5, 3, 6, 9 and 12 months post SBRT. Additional visits will be made if clinically indicated based on patient symptomatology.

4.0 PATIENT SELECTION

Patients with cancer of the head and neck who are deemed unfit for continuous course standard cisplatin based chemoradiotherapy will be eligible. Patients with squamous cell cancer (mucosal or cutaneous; p16 positive or negative), adenocarcinoma, or salivary gland cancer are eligible.

A completed patient eligibility checklist is required following the approved standard operating procedure of the enrolling institution.

4.1 Inclusion Criteria

Patients must meet all of the following inclusion criteria to be eligible for enrollment:

_____ 4.1.1 The patient must have squamous cell carcinoma, adenocarcinoma or malignant salivary gland cancer (e.g. acinic cell, adenoid cystic, mucoepidermoid, salivary duct carcinoma) proven by histologic diagnosis. Both mucosal and cutaneous cancers are eligible.

_____ 4.1.2 The patient must have clinical stage T1-4, N0-3, M0-1, stage II-IVC carcinoma as per the 7th edition of the AJCC staging manual. Patients with T1N0M0 will be ineligible. Patients with metastatic disease with a limited metastatic burden are eligible if obtaining local control is determined by their treating oncologist to be an important therapeutic goal.

_____ 4.1.3 The patient must have imaging documenting a primary tumor, or involved lymph node, $\geq 2.5\text{cm}$ in greatest dimension.

_____ 4.1.4 PET/CT is required for all patients, unless contraindicated. This may be acquired prior to study entry or after enrollment prior to SBRT planning.

_____ 4.1.5 The patient must have a history and physical documented within four weeks of registration and be deemed by a medical oncologist to be ineligible for standard continuous course chemoradiotherapy with Cisplatin, or refuse treatment with Cisplatin.

_____ 4.1.6 Performance status - Karnofsky PS ≥ 40

_____ 4.1.7 Age ≥ 18 years.

- _____ 4.1.8 Female patients can not be of childbearing age, or if they are, must have a negative pregnancy test prior to enrollment and be willing to use contraceptives during treatment and continue for 6 additional months.
- _____ 4.1.9 Patients must have the ability to understand and the willingness to sign a written informed consent document.

4.2 **Exclusion Criteria**

The presence of any of the following will exclude a patient from study enrollment.

- _____ 4.2.1 Patients with T1N0M0 stage I disease.
- _____ 4.2.2 Patients who are receiving any other investigational agents.
- _____ 4.2.3 Patients with non-malignant histology.
- _____ 4.2.4 Patients with life expectancy <6 months.
- _____ 4.2.5 Patients who cannot lie flat for 20 minutes.
- _____ 4.2.6 Patients with prior history of head and neck radiotherapy (>40Gy) with significant areas of anticipated overlap

4.3 **Inclusion of Women and Minorities**

Both men and women and members of all races and ethnic groups are eligible for this trial.

5.0 **Registration**

All subjects who have been consented are to be registered in the OnCore Database.

6.0 **TREATMENT PLAN**

6.1 **Simulation/Planning CT and Co-registration**

The patient will undergo a CT simulation for treatment planning with a recommended slice thickness of 1.5 mm, and a maximum allowed slice thickness of 3 mm. Patients will be immobilized using a 5pt aquaplast mask during the simulation. IV contrast should be used unless there is a contraindication (e.g. allergy or elevated creatinine). These images should be co-registered with the diagnostic PET/CT for planning purposes. If an MRI has been obtained, it should also be co-registered to aid in target delineation.

6.2 **Radiation Planning**

Radiation planning will utilize tissue heterogeneity corrections. The gross target volume (GTV) should be contoured and include all radiographically apparent areas of disease. There will be no clinical target volume (CTV) expansion on this volume. A planning target volume (PTV) will then be generated with a 2-3.5mm expansion of the GTV. A 2.5mm expansion is recommended but some variability is allowed for based on tumor location and motion and setup variability from patient to patient.

An optional elective CTV can be contoured and include areas thought to be at high risk of microscopic disease. This volume will be treated with 30Gy concurrently using a simultaneous integrated planning technique. While this will generally not be used for most patients, some patients with multifocal nodal disease may require more comprehensive lower dose coverage of their other nodal stations. The use of this target volume is at the discretion of the treating radiation oncologist.

The radiation dose will be prescribed to cover 95% of the PTV. Thus >95% of the PTV should receive the prescription dose (e.g. 35Gy in 5 fx). >99% of the GTV must also receive prescription dose. Rapid dose falloff outside the PTV is the priority and heterogeneity within the target is allowed. <0.03cc of tissue inside the PTV should receive >110% of the prescription dose.

[figure not shown]
Normal structures to be contoured include the brainstem, brainstem planning risk volume (PRV=brainstem +3mm) brain, spinal cord, spinal cord PRV (spinal cord +5mm) eyes, optic nerves, optic chiasm, cochlea, parotids, submandibular glands, oral cavity, lips, larynx, supraglottis, constrictors, esophagus, trachea, carotid arteries, brachial plexus.

Effort should be made to minimize the dose to these structures as much as possible. Any normal structure involved with disease should be treated fully. However, the following constraints are considered hard constraints and cannot be violated, even if this compromises tumor coverage.

- Spinal cord – <0.03cc \geq 25Gy
- Brainstem - <0.03cc \geq 25Gy
- Optic nerves - <0.03cc \geq 20Gy
- Optic chiasm - <0.03cc \geq 20Gy
- Eyes - <0.03cc \geq 25Gy
- Brachial Plexus - <0.03cc \geq 30Gy

For patients that would require inclusion of >180 degrees of involvement of the carotid artery, PTV can be contracted to allow for more aggressive carotid sparing at the discretion of the treating radiation oncologist.

Representative SBRT treatment planning images and dose volume histogram plots

